All prostacyclins have limitations impacting their safety and potential efficacy profile. Parenteral and oral IPR agonists are associated with on-target dose-limiting adverse events, including headache, jaw pain, nausea, diarrhea and hypotension, and require titration to an individual maximum tolerable dose. Nebulized iloprost and treprostinil are also dose limited by systemic adverse effects and have a relatively short duration of action, with both factors likely contributing to modest efficacy of these agents. As a result of these shortcomings, the initiation of prostacyclin therapy is delayed in some PAH patients, with a clear subsequent negative effect on prognosis (Badagliacca et al 2012).

To address these shortcomings, QCC374 has been designed as a chemically stable, selective inhaled IPR agonist for dry powder inhalation, with long duration of action (via optimized cell membrane affinity) and low systemic exposure (high plasma protein binding, rapid clearance). These characteristics are expected to lead to a considerably improved safety and tolerability profile and potentially increased efficacy compared to other members of the prostacyclin class.

Corporate Confidential Information

Corporate Confidential Information

Corporate Confidential Information

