3.7.2 Prostacyclin Associated Adverse Events

As discussed above, all marketed prostacyclins (synthetic prostacyclins, prostacyclin analogs and IPR agonists) are associated with on-target systemic adverse events, including headache, jaw pain, flushing, nausea and diarrhea. Headache, jaw pain and flushing were reported in the FIH study with QCC374. The risk of these adverse events is minimized in early clinical exploratory studies in PAH because subjects are not expected to be titrated to their individual

MTD, and the overall systemic exposure is minimized due to inhaled delivery, rapid systemic clearance and high protein binding of QCC374. If a prostacyclin associated adverse event does occur, it is expected to be mild-to-moderate in severity and transient, and the subject will be treated with standard of care (e.g. acetaminophen or ibuprofen analgesia for headache).

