3.7.4 Hemostasis

Inhibition of platelet aggregation constitutes a major physiological effect of prostacyclin, mediated via the IP receptor and cyclic adenosine monophosphate. Systemic and inhaled prostacyclins are reported to increase the risk of bleeding, particularly in patients with other risk factors for bleeding. Increased bleeding therefore represents a potential risk for QCC374.

Corporate Confidential Information

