11.5.2 Safety

Vital signs

All vital signs data will be listed by treatment, subject, and visit/time and if ranges are available abnormalities (and relevant orthostatic changes) will be flagged. Summary statistics will be provided by treatment and visit/time.

ECG evaluations

All ECG data will be listed by treatment, subject and visit/time, abnormalities will be flagged. Summary statistics will be provided by treatment and visit/time.

Clinical laboratory evaluations

All laboratory data will be listed by treatment, subject, and visit/time and if normal ranges are available abnormalities will be flagged. Summary statistics will be provided by treatment and visit/time.

Adverse events

All information obtained on AEs will be displayed by treatment and subject.

The number and percentage of subjects with AEs will be tabulated by body system and preferred term with a breakdown by treatment. A subject with multiple adverse events within a body system is only counted once towards the total of this body system.

Spirometry

All spirometry data will be listed by treatment, subject and visit/time. Summary statistics will be provided by treatment and visit/time.

Pharmacokinetics

QCC374 and QCM441 plasma concentration data will be listed by dose-level, subject, and visit/sampling timepoint. Missing data will be labeled as such in the concentration data listings.

Descriptive summary statistics will be provided by dose-level and visit/sampling time point, including the frequency (n, %) of concentrations below the LLOQ and reported as zero. Summary statistics will include mean (arithmetic and geometric), SD, CV (arithmetic and geometric), median, minimum and maximum. Concentrations below LLOQ will be treated as zero in summary statistics as well as for calculation of PK parameters. A geometric mean will not be reported if the dataset includes zero values.

Pharmacokinetic parameters will be calculated as described in [Section 8.7](#) and will be listed by dose-level, study day and subject. Descriptive summary statistics will be provided including mean (arithmetic and geometric), SD, CV (arithmetic and geometric), median, minimum and maximum. An exception to this are T_{max}, T_{min}, and T_{last} where only median, minimum and maximum will be presented. A geometric mean will not be reported if the dataset includes zero values.

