1.4 Study design and treatment

[figure not shown]
This is a non-confirmatory, randomized, subject and investigator blinded, placebo controlled study of QCC374 in PAH patients. The study will have 2 parts. In Part 1, an initial safety cohort, 8 subjects will be randomized in a 6:2 ratio and the starting dose will be 0.03 mg bid. In Part 2, approximately 30 subjects will be randomized in a 2:1 ratio, with a planned starting dose of 0.06 mg b.i.d. In both parts, subjects will be up-titrated during the first two weeks of

the study to 0.12 mg b.i.d, or to their maximum tolerated dose (MTD) if their individual MTD is below 0.12 mg b.i.d. The treatment duration is 16 weeks.

Figure 1-1: Study Periods

Figure 1-2: Part 1 and Part 2 Dose Evaluation and Titration

= dose evaluation. The investigator will assess an individual subject's clinical status and reported adverse events. The investigator will increase the dose to the next dose level *unless* he/she believes, based on their medical judgement, that the dose should not be increased due to the severity of typical pharmacologic effects of IP-receptor agonists (including headache, jaw pain, myalgia, flushing and nausea).

[#]Part 2 will begin only after a safety evaluation of Part 1, triggered when 8 subjects in Part 1 have completed 2 weeks of dosing. The safety data reviewed will include AE listings, vital signs, spirometry and ECG data. The dosing regimen in Part 2 is subject to change, based on information from Part 1.

*0.12 mg BID is the maximum dose, but a subject may continue in the study at a lower dose if 0.12 mg BID is not reached by Day 14.

2 First interpretable results (FIR)

First interpretable results (FIR) will be provided for this trial.
Corporate Confidential Information

FIR will focus on the following analyses:

- Analysis populations (if needed)
- Subject disposition

- Demographics and baseline characteristics. Baseline characteristics include, but not limited to:
 - Etiology of PAH
 - Time from PAH diagnosis
 - PVR
 - WHO FC
 - Borg Dyspnea Score
 - NT-proBNP level
 - Background PAH therapy
 - Smoking status
 - FEV1% predicted
 - Lung volumes (TLC % predicted)
 - DLco
 - Historic right catheter vs catheter at baseline
- Safety results
 - Number and percentage of subjects with adverse events by body system
 - Number and percentage of subjects on different dose levels during stable dose treatment period (0.03, 0.06, 0.12)
- Pharmacodynamic analyses will include, but are not limited to:

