The number and percentage of subjects with adverse events will be tabulated by body system and preferred term with a breakdown by treatment. A subject with multiple adverse events within a body system is only counted once towards the total of this body system and treatment. Separate tables and listings will be presented indicating event severity and study drug relationship. Tables indicating incidence/severity will also be provided with a breakdown by month.

For the legal requirements of ClinicalTrials.gov and EudraCT, two required tables on treatment emergent adverse events which are not serious adverse events with an incidence greater than 5% and on treatment emergent serious adverse events and SAE suspected to be related to study treatment will be provided by system organ class and preferred term on the safety set population.

If for a same patient, several consecutive AEs (irrespective of study treatment causality, seriousness and severity) occurred with the same SOC and PT:

- a single occurrence will be counted if there is ≤ 1 day gap between the end date of the preceding AE and the start date of the consecutive AE
- more than one occurrence will be counted if there is > 1 day gap between the end date of the preceding AE and the start date of the consecutive AE.

For occurrence, the presence of at least one SAE / SAE suspected to be related to study treatment / non SAE has to be checked in a block e.g., among AE's in a ≤ 1 day gap block, if at least one SAE is occurring, then one occurrence is calculated for that SAE.

The number of deaths resulting from SAEs suspected to be related to study treatment and SAEs irrespective of study treatment relationship will be provided by SOC and PT.

Spirometry

All spirometry data will be listed by treatment, subject and visit/time. Summary statistics will be provided by treatment and visit/time.

Pulse oximetry

Oxygen saturations (%) will be listed by treatment, subject and visit/time. Summary statistics will be provided by treatment and visit/time.

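### No patient-level count is planned for prostacyclin-type events as a class or for bleeding at any site, and the first results do not go below body system

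*SAP*

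**What the plan says.** Safety and tolerability is a secondary objective (Protocol 2.2; SAP 1.3.2). Protocol 1.1 says of the drug's design features: "These characteristics are expected to lead to a considerably improved safety and tolerability profile".

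The protocol names two risks that each cover several complaints:

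- Prostacyclin-associated events (Protocol 3.7.2), of which it says: "Headache, jaw pain and flushing were reported in the FIH study with QCC374". These events are also given as examples in the up-titration text of 3.1.1 and 3.1.2.
- Bleeding (Protocol 3.7.4): "Increased bleeding therefore represents a potential risk for QCC374".

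For the final report, SAP 7.1.2 states: "The number and percentage of subjects with adverse events will be tabulated by body system and preferred term with a breakdown by treatment". Protocol 11.5.2 has the same structure: "The number and percentage of subjects with AEs will be tabulated by body system and preferred term with a breakdown by treatment". The SAP's counting rule is: "A subject with multiple adverse events within a body system is only counted once towards the total of this body system and treatment". It adds: "Separate tables and listings will be presented indicating event severity and study drug relationship", and further tables of incidence and severity by month. The registry tables and the deaths are by system organ class and preferred term. All adverse events are also listed by treatment and subject.

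For the first interpretable results, the adverse event item in SAP 2 is: "Number and percentage of subjects with adverse events by body system".

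**The concern.** A reader weighing tolerability against the PVR result will ask two plain questions. How many patients on each arm had any prostacyclin-type event? How many bled at any site? The planned tables answer neither. They answer narrower questions, one preferred term or one body system at a time. The listed complaints (head, jaw, muscle, flushing, gut) and bleeds at different sites are not confined to one body system, so the rule of counting a patient once within a body system does not produce the class total.

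This matters because the study is meant to judge whether the clinical profile warrants further development (Protocol 1.4), and better tolerability than the class is part of the rationale. With few patients per arm, a modest excess spread over several rows could be hard to see. If the group counts are made later by hand from the listings, someone must choose which terms belong after seeing results by arm.

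**Working it through.** **1. Denominators.** Protocol 11.7 assumes about 20% dropout and about 30 completers: 30 / 0.8 = 37.5, rounded up to 38. This matches the stated figure of approximately 38. By arm (Protocol 3.1.1 and 3.1.2): QCC374 6 + 20 = 26; placebo 2 + 10 = 12; total 38.

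**2. What is counted where.**

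| Output | Single preferred term | Body system | Any prostacyclin-type event | Any bleeding |
|---|---|---|---|---|
| Final tables (SAP 7.1.2) | yes | yes | no | no |
| Severity, relationship and month tables (SAP 7.1.2) | no grouping by harm | no grouping by harm | no | no |
| First results (SAP 2) | no | yes | no | no |
| Subject listing (SAP 7.1.2) | hand count only | hand count only | hand count only | hand count only |

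No redaction is marked in SAP section 7. SAP 2 has one redaction mark, ahead of the readable list.

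**3. Can the group total be recovered from the rows?** If the terms in a group have patient counts c1, ..., ck in an arm of n patients, the number with at least one event lies between max(c) and min(sum of c, n). The documents give no event rates, so the counts below are assumptions.

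| Arm | Assumed counts on five terms | Patients with any event |
|---|---|---|
| QCC374, n = 26 | 3, 3, 3, 3, 3 | 3 to 15 (11.5% to 57.7%) |
| QCC374, n = 26 | 6, 4, 3, 3, 2 | 6 to 18 (23.1% to 69.2%) |
| Placebo, n = 12 | 1, 1, 1, 1, 1 | 1 to 5 (8.3% to 41.7%) |

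Taking the first and third rows together, the difference QCC374 minus placebo could be anything from 3/26 - 5/12 = -30.1 percentage points to 15/26 - 1/12 = +49.4 points. Even its sign is not determined. Body-system totals may narrow an upper bound, but they also include unrelated events and so do not fix the count.

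**4. Is the group membership settled?** It is not. All three lists below are open-ended, introduced as examples or as inclusions.

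| Protocol section | Events named |
|---|---|
| 3.1.1 | headache, jaw pain, myalgia, flushing, nausea |
| 3.7.2 | headache, jaw pain, flushing, nausea, diarrhea |
| 6.9 | headache, jaw pain, flushing |

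Together they name six events; only three appear in all of them.

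**5. Illustration of dilution (not a planned test).** With no placebo events in a row, the one-sided Fisher p-value for k QCC374 patients is C(26,k)/C(38,k): 0.131 for k = 5 and 0.083 for k = 6. A row of 1 to 3 patients therefore cannot stand out at 0.10.

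Assume independent bleeding risks of 6% against 1.25% in each of four body systems. Any bleeding is then 1 - 0.94^4 = 21.9% against 1 - 0.9875^4 = 4.9%. The chance of p <= 0.10 is 0.3% in a single row and about 32% for the grouped count. These figures depend wholly on the assumed rates, on independence, and on a test that the SAP does not plan.

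**The case against.** The strongest reply is that the plan already reports what its endpoint promises: adverse events, serious adverse events and all safety assessments. The preferred-term table gives the number of patients with headache, jaw pain, flushing, nausea or diarrhea by arm. Severity, relationship and month tables follow. SAP 7.1.2 also plans the proportion with a dose reduction due to an adverse event and the proportion reaching each dose. The first results are an early summary, and ongoing safety is covered by the unblinded review after Part 1 (Protocol 3.1.1) and the data monitoring committee (Protocol 10.4). The protocol defines no composite or event of special interest. With about 38 patients, a hand count is easy. A composite can also mislead by weighing mild flushing like severe nausea. Effects of one receptor mechanism may cluster in the same patients, which would reduce what grouping adds.

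Much of this stands, and it rules out three stronger readings that a reader might infer:

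- That no table shows how many patients had each harm. The final preferred-term table does so for each single term.
- That a known harm would be reported as absent. Every coded event appears in a table; at most a spread-out excess could be obscured.
- That hypotension shares the cross-system gap. It is one condition, is counted under its own term when reported, and blood pressure is summarised by treatment and visit with abnormal and orthostatic values flagged.

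What does not stand is that the existing tables or listings are enough. The tables cannot yield the group totals, and a later hand count leaves membership open when the protocol's own lists disagree. The mild-versus-severe objection is met by showing maximum severity.

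**Conclusion.** The point holds in this limited form: the readable plan has no grouped patient-level count for prostacyclin-type events as a class or for bleeding at any site, and the first results give no preferred terms. That the group totals cannot be recovered follows from overlap between terms and needs no event rate. The size of the ambiguity does depend on counts: under the assumed counts it is 3 to 15 of 26 on QCC374 and 1 to 5 of 12 on placebo. The denominators assume that about 38 patients are randomized and dosed; a larger sample after the interim analysis would change the percentages but not the argument. The exact body system of each term depends on MedDRA, which the documents do not reproduce. The Fisher figures are illustrative only and carry no weight in the conclusion. This is a worthwhile, inexpensive improvement to safety reporting in a non-confirmatory study. It does not touch the PVR analysis.

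**What to change.** In SAP 7.1.2 and in the SAP 2 list, add a table by treatment giving the number and percentage of patients with at least one on-treatment event in:

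- (a) a prostacyclin-associated group, after reconciling for analysis purposes the differing lists in Protocol 3.1.1, 3.7.2 and 6.9;
- (b) a bleeding group covering all sites.

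For each group, show maximum severity per patient and the QCC374-minus-placebo difference in percentage with an interval, stating its method and level. State the on-treatment window. Fix both preferred-term lists in the SAP before unblinding. Because the sponsor's Part 1 safety review is unblinded by design, draw the lists from the protocol text and the dictionary rather than from those data. In the first results, show preferred term as well as body system.

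The cost is a short medical review of two term lists and one or two extra tables from events already to be coded in MedDRA (Protocol 10.3). No new data are collected, and no dosing or titration rule is affected.

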3.7 Risks and benefits

Preclinical studies suggest that QCC374 may be of benefit for patients with PAH. However, QCC374 has not been studied previously in PAH patients and as such, the benefit for subjects participating in the study is unknown.

Prostacyclins, including the synthetic prostacyclin epoprostenol, the prostacyclin analogs treprostinil and iloprost, and the IPR agonist selexipag, have been associated a number of unwanted effects, including hypotension, jaw pain, flushing, headaches, an increased risk of bleeding, and gastrointestinal symptoms (nausea, vomiting, abdominal cramps and diarrhea). In addition, inhaled prostacyclin analogs have been associated with an increased risk of bronchospasm. As an inhaled IPR agonist, the potential risks of QCC374 are informed by prostacyclin adverse effects and some of these adverse events (headache, jaw pain, flushing) were observed in the FIH study, as described below. However, due to the QCC374's mode of administration, its high plasma-protein-binding (99.9% in humans) and its fast clearance, the systemic exposure to free QCC374 is very low, which is expected to minimize unwanted effects at the anticipated clinical doses. Furthermore, the data gained from the safety pharmacology and repeated dose toxicity studies, as well as FIH study, suggest a favorable safety and tolerability profile for QCC374.

The risk to subjects in this trial will be minimized by adherence to the eligibility criteria, close clinical monitoring, data review prior to beginning Part 2 and study stopping rules.

There may be unknown risks of QCC374 which may be serious and unforeseen.

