3.7.3 Risk of Bronchospasm or Cough

No compound-driven changes in the lung or effects on respiratory function were observed in the animal studies. Reversible alterations of the laryngeal epithelium were seen in the rat inhalation studies; however, similar findings are often observed in rodent inhalation studies and are considered adaptive to extended particle exposure and not test article-specific.

Increased risk of bronchospasm, wheezing and worsening of pre-existing pulmonary edema were reported with the inhaled prostacyclin analogs treprostinil and iloprost.

Corporate Confidential Information

Subjects with a history of significant underlying obstructive lung disease will be excluded from early clinical development studies in PAH. Bronchospasm will be monitored by subjective clinical data (i.e., cough, shortness of breath, and chest tightness) and objective clinical data (i.e. spirometry). In the event of clinically apparent airway reactivity/irritation, subjects will be treated with standard of care (i.e., inhaled short acting beta agonist).

Corporate Confidential Information

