7.2 Discontinuation of study treatment

Subjects may voluntarily discontinue study treatment for any reason at any time.

The investigator must discontinue study treatment for a given patient if, on balance, he/she believes that continuation would be detrimental to the subject's well-being.

Study treatment **must** be discontinued under any of the following circumstances and the reason for discontinuation must be indicated on the CRF:

- Subjects withdraws consent
- Pregnancy (see [Section 8.6](#) (Safety) and [Section 9.6](#) (Pregnancy reporting))
- Clinically significant bronchospasm reflected in spirometry assessments believed to be related to study drug
- Occurrence of adverse events which the investigator or sponsor judges unacceptable for continuation of participation in the study
- Non-compliance with the conditions of the trial and/or instructions by the investigator which could jeopardize the subject's safety or integrity of study results
- Use of prohibited treatment as per [Section 5.2](#).
- Clinical worsening of PAH:
 - A persistent decrease in 6MWD of more than 15% from baseline, confirmed by two tests on different days, believed to be due to worsening of underlying PAH*
 - Hospitalization due to persistent worsening of PAH*
 - The need for new PAH specific treatment or an adjustment in dose or type of an existing specific PAH treatment (PAH specific medications include: all endothelin receptor antagonists, phosphodiesterase 5 inhibitors, soluble guanylate cyclase inhibitors and oral, intravenous or subcutaneous prostacyclins.)*

*In the event of clinical deterioration the investigator must carefully assess if the deterioration of the subject's condition is related to the underlying pulmonary hypertension or can be explained by an alternative cause (e.g. transient infection, surgical or medical intervention other than PH related, musculoskeletal disease) and document this determination in the CRF.

The appropriate personnel from the site and Novartis will assess whether study treatment should be discontinued for any patient whose treatment code has been broken inadvertently for any reason.

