7.1.2 Descriptive analyses

Subject demographics and other baseline characteristics

All data for background and demographic variables will be listed by treatment group and subject. Summary statistics will be provided by treatment group.

Relevant medical history, current medical conditions, results of laboratory screens, drug tests and any other relevant information will be listed by treatment group and subject.

Treatment

Data for study drug administration (rescue medication) and concomitant therapies will be listed by treatment group and subject.

Summary tables will be used to present the proportion of subjects who reached each QCC374 dose, the proportion of subjects who had their dose reduced due to an adverse event, and the proportion of subjects who completed 16 weeks of treatment by dose subject received most from Day 15 to Day 112. Summary statistics for the number of days at each dose will be provided.

The proportion of subjects enrolled in the extension study will be summarized by treatment group.

Vital signs

All vital signs data will be listed by treatment, subject, and visit/time and if ranges are available abnormalities (and relevant orthostatic changes) will be flagged. Summary statistics will be provided by treatment and visit/time. Baseline visit will be used as the baseline value.

ECG evaluations

All ECG data will be listed by treatment, subject and visit/time, abnormalities will be flagged. Summary statistics will be provided by treatment and visit/time. Baseline visit will be used as the baseline value.

Clinical laboratory evaluations

All laboratory data will be listed by treatment, subject, and visit/time and if normal ranges are available abnormalities will be flagged. A separate listing is provided presenting all parameters in a subject with any abnormal values. Summary statistics will be provided by treatment and visit/time. Baseline visit will be used as the baseline value.

Adverse events

All information obtained on adverse events will be displayed by treatment and subject.

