7.1.3 Graphical presentation

Boxplots to visualize trends in longitudinal safety data (vitals, ECG, lab parameter, lung volumes) will be created. Mean (SD) plots will be used to visualize trends for spirometry and pulse oximetry.

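### Spirometry is listed by subject, but its only planned summaries are by-visit statistics and mean plots, with no baseline, change from baseline, flag or count of patients with a fall

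*SAP*

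**What the plan says.** Protocol 3.7 notes that "inhaled prostacyclin analogs have been associated with an increased risk of bronchospasm". Protocol 3.7.3 monitors bronchospasm in two ways: symptoms as the subjective part and spirometry as the objective part. Protocol 7.2 lists among the mandatory reasons to stop treatment: "Clinically significant bronchospasm reflected in spirometry assessments believed to be related to study drug". No numeric criterion is attached to that rule.

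SAP 7.1.2 gives the whole spirometry analysis in two sentences: "All spirometry data will be listed by treatment, subject and visit/time. Summary statistics will be provided by treatment and visit/time". Protocol 11.5.2 has the same content. The only figure is in SAP 7.1.3: "Mean (SD) plots will be used to visualize trends for spirometry and pulse oximetry".

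Other safety data in SAP 7.1.2 get more. For ECG it says: "All ECG data will be listed by treatment, subject and visit/time, abnormalities will be flagged", and it names the baseline visit as the reference. Vital signs and laboratory data also get flags where ranges exist, and the same baseline. Laboratory data get a further listing for subjects with any abnormal value.

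Adverse events are tabulated as number and percentage of subjects by body system and preferred term, with separate tables for severity and drug relationship.

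**The concern.** Bronchospasm is a within-patient event, likely to affect a few patients rather than shift a whole arm. A by-visit mean of raw values responds weakly to that pattern. The minimum of raw FEV1 does not rescue it, because it picks out the patient with the smallest lungs and not the one with the largest fall.

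The reference value is also undefined. Table 8-1 schedules spirometry at both screening and the baseline visit, and neither document says which one counts as baseline. Anyone counting falls from the listing after unblinding would have to choose both the baseline and the cut-off with the treatment codes known.

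At stake is how clearly the report can describe airway effects, which belong to the secondary safety objective. The primary PVR analysis is not affected.

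**Working it through.** **1. Arm sizes.** Protocol 11.7 wants about 30 patients with complete PVR data at about 20% dropout.
- 30 / (1 − 0.20) = 37.5, rounded up to 38. This reproduces the stated figure.
- Part 1 has 8 patients at 6:2 and Part 2 about 30 at 2:1 (Protocol 3.1.1 and 3.1.2).
- QCC374: 6 + 20 = 26. Placebo: 2 + 10 = 12.

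**2. How far a few falls move the arm mean.** Shift = k × fall / 26, where k is the number of patients affected and the others are unchanged. The documents give no size of fall and no spirometry SD, so the following are assumptions: a fall of 20%, an SD of percent change of 5% to 10%, a typical FEV1 of 2.0 L (so the fall is 0.4 L), and a between-patient SD of 0.5 to 0.7 L. Each shift is divided by the standard error on its own scale, SD/√26.

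| Patients with a fall | Shift in mean change | In SE (SD of change 10% to 5%) | Shift in raw mean | In SE (SD 0.7 to 0.5 L) |
|---|---|---|---|---|
| 1 | 20/26 = 0.77 points | 0.39 to 0.78 | 0.4/26 = 0.015 L | 0.11 to 0.16 |
| 2 | 40/26 = 1.54 points | 0.78 to 1.57 | 0.8/26 = 0.031 L | 0.22 to 0.31 |

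The raw column describes a mean at one visit, shown with between-patient spread, which is what the SAP plans. If the same patients attend two visits, the difference between the two raw means equals the mean change. However, the planned output gives no SD of change against which to judge it, and the set of patients alters as some stop treatment.

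**3. What a patient count would show.** Two patients on QCC374 and none on placebo would appear as 2/26 (7.7%) against 0/12. That displays the pattern but does not establish a drug effect. If two patients among 38 have a fall, the chance that both are on QCC374 by allocation alone is C(26,2)/C(38,2) = 325/703 = 0.46, the one-sided Fisher probability.

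**4. Whether the adverse event tables cover the same ground.** Under Protocol 9.1 a test result is an adverse event only if it causes signs or symptoms, is considered clinically significant, or requires therapy. A fall meeting none of these stays in the listing and appears in no count.

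**5. Side by side in the SAP.**

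| Data | Flag | Stated baseline | Plot (7.1.3) |
|---|---|---|---|
| Vital signs | Yes, where ranges exist | Baseline visit | Boxplot |
| ECG | Yes | Baseline visit | Boxplot |
| Laboratory | Yes, where ranges exist, plus extra listing | Baseline visit | Boxplot |
| Spirometry | None stated | None stated | Mean (SD) |

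SAP 7.1.3 also gives boxplots, which display spread and outliers, to lung volumes, which the schedule collects only at screening. The repeated airway measure gets means.

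**The case against.** The strongest reply is that individual falls are already visible. The spirometry sentence itself plans a listing by subject and visit, and about 38 patients can be read through. Bronchospasm that leads to stopping would normally be reported as an adverse event and counted per arm. The reason for stopping goes on the CRF, and medication used to treat adverse events is recorded and listed. Safety during the trial does not wait for this table either: the sponsor's unblinded Part 1 review includes spirometry (Protocol 3.1.1), and a data monitoring committee reviews safety regularly (Protocol 10.4).

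All of this stands. A reader might infer that spirometry is reported only as group statistics, that individual falls cannot be seen, or that the airway part of the safety objective cannot be answered. The documents do not support those readings, because of the listing and the adverse event tables. Nor do they say that conclusions would rest on mean curves alone.

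It is also fair that loss of affected patients from later means is common to any on-treatment summary. It is partly offset here: patients who stop are not withdrawn unless they withdraw consent (Protocol 7.2), and the schedule footnotes ask for an attempt at the Day 113 assessments. A Day 113 value after stopping does not replace the last on-treatment value, though. Finally, SAP 1.1 refers to wider reporting documents that are not public and may specify more.

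What the reply leaves open is narrow: an unflagged listing has no baseline or cut-off fixed in advance, and the adverse event tables depend on investigator judgement, which the objective measurement is meant to supplement.

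**Conclusion.** The point holds as a gap in safety reporting. Spirometry is the stated objective monitor for a named risk, yet it has no planned baseline, change from baseline, flag or count of patients with a fall, while vital signs, ECG and laboratory data have flags and a baseline.

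Under the assumptions above, two 20% falls among 26 patients move the mean by 0.8 to 1.6 standard errors on the change scale and 0.2 to 0.3 on the raw scale at one visit. The planned summaries are therefore insensitive to a few falls, not blind to them. The sizes depend on assumed falls and SDs; the missing definitions do not.

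The study is small and non-confirmatory, so the added counts would describe and not test, as the 0.46 shows. The change is worth making because it is cheap and captures falls that need not become adverse events.

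**What to change.** Before unblinding, amend the spirometry paragraph of SAP 7.1.2 to:
- define the pre-dose baseline-visit value as the spirometry baseline, in line with vital signs, ECG and laboratory data;
- summarise percent change from baseline in FEV1 and FVC by treatment and visit, including the Day 1 post-dose test where collected. Table 8-1 shows this test for Part 1; the spirometry row of Table 8-3 cannot be read in the text available, although its footnote on timing after dose is present;
- report each patient's lowest on-treatment value, including the last value before stopping treatment;
- flag falls in the subject listing;
- tabulate the number and percentage of patients per arm whose fall exceeds reporting categories that the sponsor fixes in advance. These are descriptive only and do not alter the stopping rule in Protocol 7.2 or any other care decision.

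The data are already collected and processed centrally (Protocol 10.3), so the cost is SAP wording, a listing flag and one extra descriptive table. The table should carry a note that its counts are too small for formal comparison between arms.
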